Outline of Design: Approximately 235 Child-Pugh Class A or B7 patients with HCC will be enrolled into this study. In Parts A and B, patients were initially randomly assigned onto 1 of 2 doses, balanced based on AFP levels (≤ 400 ng/mL and >400 ng/mL), etiology, and whether sorafenib-naïve or not. A planned interim analysis after approximately 10 (for PK and acute safety) patients enrolled into each dose and completed 1 cycle was carried out. The second interim analysis for futility of 1 or both doses was not carried out but, as part of the continuous monitoring of safety, PK, and laboratory markers in patients with HCC, the sponsor noted that patients in both cohorts were staying on study beyond 4 months. An additional data review was carried out based on 64 enrolled patients, and a decision was made to stop enrollment to the 160 mg/day dose and continue enrollment to the 300 mg/day dose until 70 patients were treated. The protocol was amended (Amendment [b]) to have 3 parts. The 2 cohorts planned in the original protocol and in Amendment (a) were designated as Part A. Part B enrolled approximately 40 patients with AFP levels <1.5 x ULN and treated them with 300 mg/day intermittent dosing. Two interim analyses were planned for Part B – one after the last of 70 patients with elevated AFP levels in Cohort 2 started Cycle 1, and the second after 18 patients enrolled into Part B and were actively followed for at least 3 months or discontinued from study treatment. Part C enrolled approximately 47 Child-Pugh Class A patients and consisted of a safety lead-in of 2 dose-escalation cohorts followed by an expansion cohort where the selected dose(s) of the combination treatment were evaluated. Part D will enroll approximately 18 Child-Pugh Class A patients into 2 dose-escalation cohorts. Part E will initially enroll up to approximately 23 patients. This would give a total of approximately 235 patients enrolled.

Safety: Summary statistics, plots, and listings for all safety data collected will be provided in aggregate and by dose in Part A and Part C, and in aggregate for Part B separately. Comparisons between doses and parts will be summarized for Part A and Part B, and may be compared to Part C. Data from Part D and Part E will be summarized separately from the data in Parts A, B, and C.

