5.1.5.2. JBAK: Brief Summary of Results to Date

At the time of Amendment (e), Part A and Part B of the study have completed. A total of 149 patients were enrolled (109 in Part A and 40 in Part B). Eighty-five percent of patients were male and the median age was 65 years. Fifty-six percent of patients had an ECOG performance status (PS) of 0 and 44% had a PS of 1. Eighty-six percent of patients had a Child-Pugh Class A score and 14% had a Class B score. Etiology of disease was as follows: hepatitis C 24%, hepatitis B 20%, alcohol 20%; multiple 9.4%. Overall, 83% of patients had received prior sorafenib. Eleven patients discontinued treatment due to AEs: 8 were considered related to study treatment. Grade 3/4 AEs possibly related to treatment were observed in 26 (17%) patients. Of these AEs, neutrophil count decrease was observed in 4 patients. Anemia, hypoalbuminemia, decreased bilirubin, fatigue and embolism were observed in 2 patients each. All other AEs occurred in just 1 patient. Median TTP was 11.9 weeks (95% CI: 6.3, 12.6) in Part A and 18.0 weeks (95% CI: 10.0, 24.0) in Part B. Median OS was 31.4 weeks (95% CI: 22.9, 40.6) in Part A and 73.0 weeks (95% CI: 45.4, 104.7) in Part B. The median OS for the overall population was estimated as 40.4 weeks (95% CI: 31.1, 52.4) (Giannelli et al. 2016).

Enrollment into Part C has completed and maturation of the data is awaited. Enrollment is ongoing in Part D of the study.

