5.3.9. Safety Analyses

5.3.9.1. Study Drug Exposure

The number of cycles completed per patient and dose intensity will be summarized using descriptive statistics (mean, median, minimum, and maximum).

Dose intensity for LY2157299 is derived according to the following formula:

- Planned cumulative dose (mg):

$$PLC_i = \text{number of cycles} * \text{assigned dose per day} * 14$$

where 14 is the planned number of dosing days per cycle.

- Prescribed cumulative dose (mg):

PRC_i = sum of prescribed dose multiplied by the number of dosing days in that cycle over all cycles.

The actual dosing is collected on days 1, 12, 13, and 14 of cycle 1 and day 1 of cycle 2, which aligns with the PK sampling day. Any dose modifications collected during the treatment period will be considered in the calculation of prescribed cumulative dose. Additional and/or detailed considerations for deriving of prescribed cumulative dose will be included in the TFL requirements. For interim data cut, the number of cycles up to the last completed cycle for patients in active treatment will be considered for this calculation; for patients that has discontinued from treatment, the number of cycles up to the last cycle will be considered.

- Dose intensity in percent:

$$PDC_i = (PRC_i / PLC_i) * 100\%$$

For each patient, dose intensity for LY2157299 will be listed based on cumulative doses received during study. Note prescribed dose is the same assigned dose if there is no dose modification. Listings of dose assignment and dose information on LY2157299 will also be provided.

Cycle delays, dose reductions, and dose omissions of LY2157299, including reasons, will also be listed. If the reason for dose modification is due to AE, the associated AE will be provided. The number and percentage of patients with any dose modifications will be summarized for the entire treatment period as well as for each cycle.

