5.3.9.2. Adverse Events

The adverse events will be reported in CTCAE terms using CTCAE Version 4.0x. Any listings or summaries using MedDRA will use preferred terms in the most current version of MedDRA at the time of reporting. The version of MedDRA used in any reports will be documented.

Treatment-emergent adverse events (TEAEs) are defined as follows:

- Any AE, regardless of causation, that were not present prior to first dose and emerges on or after the day of the first dose of study treatment
- Or any PEC (emerged prior to informed consent) or any AE (emerged after signed informed consent) that were still present prior to first dose but has increased in severity (CTC grade) following the start of treatment, regardless of causation.

A listing of all adverse events by patient, including pre-existing conditions, will be presented. This listing will include patient number, adverse event (actual term, CTCAE term, and preferred term), event start and end dates, CTCAE grade, relationship to study drug/procedure, seriousness, and outcome. A listing of SAE will be produced using the same format.

Adverse events will be summarized by frequency counts and percentages as follows:

- Patients with at least one AE
- Patients with at least one TEAE
- Patients with at least one grade 3 or 4 AE
- Patients with at least one SAE
- Patients who discontinued due to AE
- Patients who discontinued due to SAE
- Patients who died on therapy
- Patients who died within 30 days of last dose of study drug

For each category above, frequency counts and percentages will also be provided for patients who had events possibly related to study drug.

Adverse events in CTCAE terms will be also be summarized by CTCAE grade within the SOC. This summary will be provided for all adverse events with CTCAE grade, regardless of causation, and repeated for possibly drug related AE with CTCAE grade.

TEAEs will be summarized by CTCAE term in decreasing frequency within the SOC, regardless of causation, and repeated for TEAEs that are deemed by investigator to be possibly study drug related. Serious adverse events will summarized in the same format.

A listing of patient discontinuation due to AE or death will also be provided.

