Chi-squared test may also be performed to compare AE incidences between the 2 doses and study parts adjusting as necessary for baseline AFP levels or other important variables. Any significant differences (p-value <0.05 or p-value < 0.01) will be indicated in the summaries.

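### Adverse event percentages are compared between study Parts with no allowance for time at risk, although exposure probably differs by Part

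*SAP*

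**What the plan says.** SAP 5.3.9.2 sets the AE measure: "Adverse events will be summarized by frequency counts and percentages as follows", followed by categories of patients with at least one event. The comparison is optional: "Chi-squared test may also be performed to compare AE incidences between the 2 doses and study parts adjusting as necessary for baseline AFP levels". The same sentence then admits further variables without naming them. Its result is marked in the tables: "Any significant differences (p-value <0.05 or p-value < 0.01) will be indicated in the summaries".

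Protocol 12.2.12 is also optional and also speaks only of a difference in incidence. The comparison of Parts as such is firmer. The protocol synopsis (Safety) says: "Comparisons between doses and parts will be summarized for Part A and Part B, and may be compared to Part C".

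Exposure appears separately, in SAP 5.3.9.1: "The number of cycles completed per patient and dose intensity will be summarized using descriptive statistics". Neither document plans an AE rate per patient-time, a time-to-first-event analysis of AEs or a common time window for comparing AEs between Parts.

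Under the synopsis, treatment continues until progression, death or discontinuation. From Amendment (b), which added Part B, asymptomatic patients may stay on drug after radiological progression (Protocol 10.1). Protocol 5.1.5.2 reports: "Median TTP was 11.9 weeks (95% CI: 6.3, 12.6) in Part A and 18.0 weeks (95% CI: 10.0, 24.0) in Part B".

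**The concern.** The chance that a patient has at least one AE grows with the time that patient is observed. When patients are treated until progression, a group that progresses later has more time in which to have an event. Two Parts with the same event rate can then show different percentages, with the longer-treated Part looking more toxic.

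The permitted adjustment does not address this. Exposure is not named, and baseline AFP cannot separate Part A from Part B because an AFP threshold defines those Parts (Protocol 8.1, criterion 3). The test could be repeated over many AE terms, and the resulting flags would tend to point the same way. What is at stake is how the safety of the Parts is described relative to each other.

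**Working it through.** **Plan's own figure.** The documents give no error rate or power for the AE comparison. The one AE percentage that can be checked is in Protocol 5.1.5.2: 26/149 = 17.4%, against the stated 17%.

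**Inputs.**
- Part A 300 mg cohort, n=72 (Protocol 12.1); Part B, n=40 (Protocol 7.1).
- Median TTP 11.9 and 18.0 weeks (ratio 18.0/11.9 = 1.51), used as a proxy for time on drug. The 11.9 weeks is for all of Part A (109 patients) and is assumed to apply to the 300 mg cohort.
- AEs collected for 30 days after treatment (Protocol Table JBAK.10): w = 30/7 = 4.29 weeks.
- Assumed: exponential time on drug, and the same constant AE hazard h in both Parts.

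**Formula.** With λ = ln2/median, P(at least one AE) = 1 − [λ/(λ+h)]·exp(−h·w). Here λ is 0.0582 per week in Part A and 0.0385 in Part B.

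For h = 0.03 per week, exp(−0.03×4.29) = 0.879.
- Part A: 1 − (0.0582/0.0882)×0.879 = 42.0%.
- Part B: 1 − (0.0385/0.0685)×0.879 = 50.6%.

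The flag rate is the exact binomial probability that an uncorrected Pearson chi-squared test gives p<0.05.

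| h per week | Part A | Part B | Difference (points) | Flagged |
|---|---|---|---|---|
| 0.01 | 18.2% | 23.9% | 5.7 | 11.9% |
| 0.02 | 31.7% | 39.6% | 7.9 | 13.9% |
| 0.03 | 42.0% | 50.6% | 8.6 | 14.5% |
| 0.05 | 56.6% | 64.9% | 8.3 | 13.2% |

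Nearly all flags call Part B worse. With equal true incidence the same test flags about 5%. Leaving out the 30-day window raises the flag rate to 13.8-18.3%.

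**Sensitivity to the proxy.** The TTP intervals overlap (6.3 to 12.6 v 10.0 to 24.0 weeks). With the 30-day window:
- medians of 11.9 v 12.6 weeks: about 5% flagged, so no visible bias;
- 12.6 v 10.0: the direction reverses;
- 11.9 v 24.0: 26-33% flagged.

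**Sensitivity to AE timing.** Assume instead a hazard of 0.05-0.1 per week in the first 4 weeks and 10-20 times lower afterwards, equal in both Parts. The crude test then flags about 6-7%.

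**Candidate remedies.** Incidence in the first 8 weeks (two 28-day cycles) is 20.4% v 20.7% at constant h = 0.03. The flag rate stays at about 5% under both hazard shapes.

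A Poisson rate comparison is correct under a constant hazard but not when AEs come early. With a hazard of 0.05 falling to 0.005 per week, incidence is 24.7% v 27.6% over mean times at risk of 16.8 v 22.7 weeks. The rates are 0.0147 and 0.0122, a ratio of 0.83 although the hazards are identical. Across the early-clustered cases the ratio is about 0.8 and roughly 10-18% of comparisons are flagged, now making the longer-treated Part look safer.

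**The case against.** The strongest reply is that the plan binds itself to little. The test is optional, the adjustment clause leaves room for other variables, and a stratified (Mantel-Haenszel) chi-squared test could handle AFP categories. Cycles completed are summarised, AE start and end dates are listed, and SAP 5.3.11 adds event counts by treatment group, so a report could derive rates. All of this is true. But time at risk is still not named, and the percentages by Part carry the same distortion without a p-value.

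The size is also open to challenge. No treatment duration by Part is given. TTP censors deaths, treatment can outlast progression, and the hazard may not be constant. Disease-related events in Part A, where OS and TTP were shorter, could offset or reverse the effect. These objections stand, and they limit the result to a conditional one.

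A reader might infer three stronger things that the documents do not support:
- That the 160 v 300 mg comparison is biased in the same way. Protocol 5.1.7 saw no difference between doses in the number of patients staying beyond 4 months.
- That the distortion drives the dose recommendation. Part A 300 mg and Part B receive the same dose, 300 mg/day was chosen at Amendment (b), and combination doses were escalated on Cycle 1 toxicity, which is already a common window.
- That combination v monotherapy is distorted by a known amount. No Part C duration or TTP is reported, and that contrast is also confounded by sorafenib and line of therapy.

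**Conclusion.** The concern holds for comparisons between Parts, chiefly Part A v Part B. The plan compares patient percentages with no allowance for time at risk, and the TTP medians suggest longer exposure in Part B. If time on drug follows TTP and the AE hazard is constant and equal, Part B appears about 6 to 9 points worse, and about 12 to 14.5% of comparisons are flagged instead of 5%. With AEs clustered early the excess is small; with similar exposure, which the TTP intervals allow, it is close to zero. The actual bias therefore cannot be stated from these documents. The change is still worth making, because it is cheap and holds the false-flag rate near 5% under both hazard shapes tried.

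**What to change.** In SAP 5.3.9.2, keep the crude incidence tables. For any comparison between Parts, base the test and any flag on AE incidence in a common early window, for example Cycles 1-2. Beside it, show first-event rates per patient-time descriptively, with time at risk running to the event or to 30 days after the last dose.

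Do not make a Poisson model the sole analysis, since it assumes a constant hazard. Do not adjust Part A v Part B for baseline AFP, which defines those Parts.

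The cost is SAP wording and one or two extra table columns, using AE and dosing data already collected. The windowed comparison ignores late events; these remain visible in the crude table.

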5.1.7. Rationale for Amendment (b)

The protocol is amended for the following reasons:

As part of the continuous monitoring of safety, PK, and laboratory markers in patients with HCC, the sponsor noted that patients are staying on study beyond 4 months. Furthermore, the 300 mg/day dose appears to have no evidence of increased toxicity. There appears to be no difference in the number of patients at the 160-mg/day and the 300-mg/day dose who stayed beyond 4 months. In addition, in all other ongoing trials with LY2157299, the dose of 300 mg/day was selected for future clinical development.

Preliminary PK data from the first interim analysis (n=20 patients) suggest that patients administered 300 mg/day have higher exposures than previously observed for the same dose level (Study JBAH) during the treatment period. LY2157299 appears to be fully eliminated after the 14-days off period of a cycle (additional PK sampling is added to study the clearance of LY2157299). The lowest exposure level (ie, most conservative) in the most sensitive nonclinical species administered LY2157299 in a clinically relevant dosing schedule (2 weeks on/2 weeks off) in which cardiac effects were observed was 24 $\mu\text{g}\cdot\text{hr}/\text{mL}$ (Table JBAK.2). The findings at this dose level (150 mg/kg) consisted of a single male rat (n=10/group) with minimal inflammation in the aortic valve and ascending aorta. Administration of 300 mg/day to patients with HCC may result in higher than anticipated exposures; however, due to the clinical safety profile observed thus far and the benefit:risk in this patient population, this approach is considered acceptable.

Because of these reasons and the lack of substantial evidence that the 160-mg/day dose is superior to the 300-mg/day dose, the dose of 300 mg/day is selected for the continuation of this trial.

For Part B, it was decided to evaluate the effects of LY2157299 in patients with AFP <1.5x upper limit of normal (ULN) to have an overall assessment of LY2157299 efficacy in all HCC patients. At the time of the decision to focus on the 300-mg/day dose, 74 patients were randomized.

The study design will be modified as follows:

- Part A: Evaluation of LY2157299 in Child-Pugh A or B7 patients with AFP $\geq 1.5x$ ULN. After stopping the 160-mg/day dose arm, all newly enrolled patients will be treated at the 300-mg/day dose.
- Part B: Evaluation of LY2157299 in Child-Pugh A or B7 patients with AFP <1.5x ULN

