With Amendment (c), the study planned to enroll approximately 190 patients: 109 patients have been enrolled in Part A (37 in Cohort 1, 72 in Cohort 2); 40 are planned for Part B, and 40 for Part C (amended to enroll Child Pugh A patients who had not received any prior systemic therapy and were to be treated with LY2157299 plus sorafenib in a safety lead-in followed by an expansion at the selected dose).

With Amendment (d) and the addition of Part D, an additional 15 patients may be enrolled. With Amendment (e) and the addition of Part E, approximately 23 additional patients may be enrolled.

The primary objective of the study now is to characterize the TTP distributions, the effect on TGF- β -associated serum biomarkers (for example, TGF- β , AFP, E-cadherin) and the relationship between biomarker response and efficacy endpoints of:

- 1) Each of the 2 doses of LY2157299 in second-line patients or patients ineligible to receive sorafenib with HCC who have elevated AFP levels (Part A, Cohorts 1 and 2),
- 2) In second-line patients or patients ineligible to receive sorafenib with HCC who have AFP levels $<1.5x$ ULN dosed at 300 mg/day (Part B),
- 3) In first-line patients with HCC treated with 2 doses of LY2157299 in combination with sorafenib. If the decision in Part C is to use only 1 treatment group in the expansion cohort, the results from patients at the other dose will simply be listed.
- 4) In second-line patients with HCC treated with LY2157299 given for 21 days on followed by 7 days off (Part E).

For efficacy endpoints, no formal hypothesis testing based on a priori power calculations is planned; rather differences in various endpoints (eg, hazard ratios for TTP, OS) between appropriate treatment groups will be estimated. Since Part C patients are different in 2 ways from patients in Parts A and B (first-line versus second-line and treated with LY2157299 in combination with sorafenib compared to LY2157299 monotherapy, respectively), the only estimate of differences between Parts A and/or B with Part C will be between Part C and the sorafenib-naive patients from Parts A and B. The interpretation of any estimate will be considered in light of the size of this subgroup.

Data from patients from Part D and E will be summarized separately from the data in Parts A, B, and C.

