12.2.12. Safety Analyses

Adverse event (AE) terms and severity grades will be assigned by the investigator using CTCAE v4.0. AE terms will also be derived from verbatims using the Medical Dictionary of Regulatory Activities.

All patients who received LY2157299 will be evaluated for safety. Safety analyses will include, but are not limited to, the following:

- all reported AEs, including seriousness, severity, and possible relationship to study drug, using CTCAE terminology and grades
- TEAEs, including seriousness, severity, and possible relationship to study drug, using CTCAE terminology and grades
- dose adjustments for any study therapy

- physical exam and other safety observations, including those specifically targeting monitoring for cardiac safety
- laboratory measures

Safety analysis may also estimate the difference in the incidence of AEs between the 2 doses and study parts, adjusting as necessary for baseline AFP levels or other important covariates.

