5.3.3. General Considerations

All patients who have received at least 1 dose of study drug will be evaluated for safety, efficacy, toxicity, and pharmacodynamic endpoints. The pharmacodynamic responses will focus on the AFP kinetics and the TGF- β 1 levels but also include the assessments of EMT associated markers (for example, E-cadherin) and fibrosis-related blood markers.

Patients with measurable disease will be included in summaries of tumor response. Tumor response will only be tabulated for patients who received at least 1 dose of study drug and have measurable disease at baseline.

After Amendment (b), patients are allowed to continue on study treatment at the investigator's discretion, even when objective progression is determined by radiological measurements, if they do not have overall symptomatic deterioration as well. This change should not affect the primary objective (estimation of TTP), PFS, or response rate. However, bias may be introduced in the assessment of OS, since patients prior to Amendment (b) will have discontinued based on objective progression alone. Therefore, patients discontinued from objective progression prior to the amendment (b) will be considered separately from those that discontinued due to objective progression or overall symptomatic deterioration after the amendment in the assessment of OS.

Patients from all sites will be pooled for all analyses. All tests of treatment effects will be conducted at a 2-sided alpha level of 0.10, unless otherwise stated. Patients with Child-Pugh Class A and B7 will be considered as 1 group of patients, given the similarity of Class B7 patients to Class A patients. If all patients in Part A and Part B are second-line, Part C patients will be analyzed as a separate group. If there are some first-line patients in Part A or Part B, different subgroups may be considered.

Efficacy:

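### SAP 5.3.9.2 plans only an optional, low-power chi-squared flag to compare AE incidence between 160 and 300 mg/day, and no risk difference with a confidence interval

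*SAP*

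**What the plan says.** SAP 5.3.9.2 first summarises adverse events as counts and percentages. The categories include Grade 3 or 4 events, SAEs and discontinuations, each repeated for events possibly related to study drug. SAP 5.3.3 has safety data shown by dose within Part A. On the comparison itself, SAP 5.3.9.2 says "Chi-squared test may also be performed to compare AE incidences between the 2 doses and study parts", adjusting for baseline AFP or other variables where necessary, and then: "Any significant differences (p-value <0.05 or p-value < 0.01) will be indicated in the summaries". It mentions no risk difference, ratio or interval.

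Protocol 12.2.12 describes the same comparison as estimation: "Safety analysis may also estimate the difference in the incidence of AEs between the 2 doses and study parts". Protocol 12.2.1 fixes the confidence level for treatment effects at a two-sided alpha of 0.10. The matching sentence in the SAP concerns tests rather than intervals: "All tests of treatment effects will be conducted at a 2-sided alpha level of 0.10, unless otherwise stated". For response rate and clinical benefit rate, SAP 5.3.8.1 does require odds ratios with 90% intervals beside the chi-squared p-value.

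**The concern.** One secondary objective is to recommend doses for future trials, so how much toxicity the higher dose might add is a question the report should bound. Two percentages show the observed gap but not its uncertainty. A flag shows only whether a threshold was crossed. If nothing is flagged, the reader learns neither the size of the excess that remains possible nor how likely the test was to find one. The SAP supplies an interval for binary efficacy endpoints, but not for harms, where failing to detect a difference is the more worrying error.

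**Working it through.** The documents state no power for the AE comparison, so there is no planned figure to reproduce.

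**Inputs**
- Patients per dose: "109 patients have been enrolled in Part A (37 in Cohort 1, 72 in Cohort 2"), from Protocol 12.1. Cohort 1 is 160 mg/day and Cohort 2 is 300 mg/day.
- Event rate: "Grade 3/4 AEs possibly related to treatment were observed in 26 (17%) patients", from Protocol 5.1.5.2. The denominator is in the same section: "A total of 149 patients were enrolled (109 in Part A and 40 in Part B"). Check: 26/149 = 17.4%, which matches.
- Flag level: 0.05, taken as two-sided. A p-value below 0.01 is also below 0.05, so the 0.05 level decides whether a difference is flagged at all.
- Assumption: the documents give no rates by dose, so the 160 mg/day rate p is varied and the 300 mg/day rate is set at 2p.

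**Which doubling fits 26 of 149?** Part B was also treated at 300 mg/day, so there are 72 + 40 = 112 patients at that dose. If Part B shares the Part A rate at 300 mg/day, 37p + 112 × 2p = 261p = 26. Then p = 26/261 = 10.0% and 2p = 19.9%. If instead 17.4% is the overall rate in Part A alone, (37 + 144)p = 0.1745 × 109 = 19.02, so p = 10.5% and 2p = 21.0%. By contrast, 17% v 34% implies 0.17 × 37 + 0.34 × 72 = 6.3 + 24.5 = 30.8 patients in Part A alone, more than the 26 reported for Parts A and B together.

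**Chance that the flag misses a doubling at 37 v 72.** This enumerates two independent binomials and applies the uncorrected Pearson chi-squared test. Only rejections with the higher rate at 300 mg/day count as detection. Miss rate = 1 − power.

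| True rates, 160 v 300 mg/day | Missed at 0.05 | Missed at 0.10 |
|---|---|---|
| 5% v 10% | 1 − 0.121 = 88% | 1 − 0.211 = 79% |
| 10% v 20% | 1 − 0.265 = 73.5% | 1 − 0.385 = 61.5% |
| 10.5% v 21% | 1 − 0.279 = 72% | 1 − 0.401 = 60% |
| 17% v 34% | 1 − 0.468 = 53% | 1 − 0.609 = 39% |
| 20% v 40% | 1 − 0.567 = 43% | 1 − 0.702 = 30% |
| 25% v 50% | 1 − 0.727 = 27% | 1 − 0.819 = 18% |

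A normal approximation agrees closely: power is 0.243 at 10% v 20% and 0.460 at 17% v 34%. With Yates' correction, which the SAP neither requires nor excludes, the miss rate at 10% v 20% rises to 1 − 0.169 = 83%. Power at the 0.05 level reaches 50% once the 160 mg/day rate is about 18%.

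**What an interval would show** (Wald, two-sided 90%)
- Both doses observed at 17%: half-width = 1.645 × √[0.17 × 0.83 × (1/37 + 1/72)] = 1.645 × 0.0760 = 0.125, so −12.5 to +12.5 points.
- Observed 10% v 20%: standard error = √(0.10 × 0.90/37 + 0.20 × 0.80/72) = 0.0682. The interval is 10 ± 1.645 × 6.82 = 10 ± 11.2, so about −1 to +21 points. That describes the data far better than the absence of a flag.

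**The case against.** The strongest reply is that the SAP does not rest the toxicity comparison on flags. The test is optional and comes on top of by-dose counts and percentages, and from those counts anyone can compute a difference and an interval. That is right. A reader might infer that tolerability is to be judged from the flags alone, but SAP 5.3.3 and 5.3.9.2 do not say so.

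Three other stronger readings are tempting and also fail.
- A reader might infer that the SAP replaces the protocol's method. The protocol's estimate is itself optional. The SAP leaves it out but does not forbid it.
- A reader might infer that Amendment (b) already reached a dose conclusion in this way, because Protocol 5.1.7 says "the 300 mg/day dose appears to have no evidence of increased toxicity". That section reports no test. It cites continuous monitoring and gives further reasons for the choice, and it discloses higher exposure than previously seen at that dose.
- A reader might infer that holding harms to 0.05 or 0.01 contradicts the 0.10 level used elsewhere. The 0.10 rule gives way where another level is stated, and a tighter flag is defensible across many AE terms. At 10% v 20%, moving to 0.10 would still miss 61.5%.

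The practical reach is also limited. This SAP was approved in October 2013. By Amendment (e), Parts A and B were complete, and Protocol 12.2.8 refers to later SAP versions that are not among these documents.

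What remains is that the only inferential AE output the SAP names has low power and carries no estimate of uncertainty.

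**Conclusion.** The point holds as a cheap improvement to the safety reporting; it does not show that the safety analysis is invalid. At 37 v 72 patients, an absent flag cannot be taken as evidence that the two doses are similarly toxic. For a doubling consistent with the reported 26 of 149, about 10% v 20%, the 0.05 flag misses it about 73.5% of the time.

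The size depends on the assumed base rate. The miss rate is only just above half at 17% v 34%, and falls below half once the 160 mg/day rate reaches about 18%. It would therefore be wrong to say without a stated rate that the flag misses a doubling more than half the time. The figures also assume an unadjusted, uncorrected chi-squared test and independent patients, and the true split by dose is not in the documents.

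**What to change.** In SAP 5.3.9.2, or in the SAP version or study report that now governs Part A, add the 300 minus 160 mg/day risk difference with its two-sided 90% confidence interval for a short list: possibly related Grade 3/4 AEs, SAEs, discontinuations due to AE, and cardiac disorders. Add one sentence saying that an absent flag is not evidence of similar toxicity. The flags may stay.

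This uses the estimate that Protocol 12.2.12 permits at the confidence level that 12.2.1 sets. The choice of categories is this review's suggestion and does not come from the protocol. It needs one extra table and no new data. The drawback is that the intervals will look wide, but that width is what the reader needs to see. They will reflect sampling error only: 160 mg/day closed early and enrolment at 300 mg/day continued, so not all of the 72 patients were randomised alongside the 37.
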